## 5. ENDPOINTS

### 5.1 Primary Endpoints

1. Isolation of epithelial cells in order to generate models of the main populations of liver cells in a three-dimensional culture environment, called organoids, and molecular characterization of the generated models. Isolation of stellate cells and their phenotypic and molecular characterization. Generation of assemblyloids that mimic the hepatic tissue architecture and its phenotypic and molecular characterization to study the onset and development of steatohepatitis.
2. Evaluation of the impact of the I148M variant (evaluation of possible combinations both in epithelial cells - hepatocytes and in stellate cells) on the steatohepatitic phenotype in human liver assembloids, with particular reference to:
  - Lipid accumulation in hepatocytes (quantitative and qualitative analysis)
  - Lipotoxicity and expression of inflammatory markers (gene expression)
  - Activation of fibrogenesis (assessment of the activation state of stellate cells, retinol metabolism and extracellular matrix deposition)

Steatohepatitis will be defined in the simultaneous presence of all these alterations in the assemblage.

3. Analysis of variants of the TM6SF2, MBOAT7 and GCKR genes, previously correlated with the development of non-alcoholic steatohepatitis (14).

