## 7. STATISTICAL ANALYSIS

### 7.1 Sample size and data analysis

The sample size was estimated in view of achieving the two primary outcomes of the project.

Previously published works (24, 25, 26, 27) have shown that the generation efficiency of liver organoids is approximately 100% starting from surgical resections and 33% from biopsies (24, 25).

Considering these estimates, in order to isolate at least 20 independent organoid cultures of each type of condition of interest in our study, we estimate to recruit at least 30 donors for each genetic variant. The intent is to obtain replicates for the analyses with a sufficient representation of the different stages of liver damage (normal liver, inflammation/fibrosis and hepatocellular carcinoma) and to be able to map the impact of the main most common inherited genetic variants (present in at least 20% of individuals) in the population.

For the first primary outcome, the primary analyses will be conducted from single-individual cell cultures. Given the descriptive nature of mapping cellular phenotypes and gene expression, and the large number of organoids ( $>10^3$ ) and cells ( $>10^9$ ) from a single individual, we will have sufficient statistical power (>80%) to identify and analyze specific cellular subsets representing >1% of the overall population.

As regards the second primary outcome, although there are important limitations in the estimate inherent to the type of project and linked to the uncertainty regarding the final characteristics of the model that will be developed during the project, we expect to observe a progressive increase in the

presence and severity of the steatohepatitis phenotype in organoids with increased number of PNPLA3 I148M variants. In particular, we estimated that we could reach a statistical power of 95% (alpha 0.05, two-tailed test) to observe a frequency of steatohepatitis phenotype of 75% vs. 25% in assemblyloids with extreme PNPLA3 genotypes, homozygous for the at-risk variant vs. wild-type (20 cases vs. 20 controls), which is consistent with the increased risk observed in clinical cohorts (28).

Statistical analyses will be performed using JMP (SA, Cary, NC) and R (<https://www.r-project.org>) software and statistical comparisons will be made using the one-way ANOVA or chi-square test, where appropriate. P values < 0.05 will be considered statistically significant.

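### The 95% power stated for the second primary outcome (75% vs 25%, 20 vs 20) is about 90% under either test the protocol names

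*Protocol*

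**What the plan says.** Protocol section 7.1 sizes the second primary outcome, the effect of the PNPLA3 I148M variant on the steatohepatitis phenotype, by comparing the two extreme genotypes. The groups are "homozygous for the at-risk variant vs. wild-type (20 cases vs. 20 controls"). The planned difference is given as "to observe a frequency of steatohepatitis phenotype of 75% vs. 25"%, and the claim is "we estimated that we could reach a statistical power of 95% (alpha 0.05, two-tailed test"). That sentence names neither a test nor a formula.

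The last paragraph of the same section says that "statistical comparisons will be made using the one-way ANOVA or chi-square test, where appropriate", with P below 0.05 counted as significant. No other test appears in the section.

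Section 5.1 makes the phenotype a yes/no result: "Steatohepatitis will be defined in the simultaneous presence of all these alterations in the assemblage".

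**The concern.** The outcome being powered is a frequency of a phenotype that is either present or absent, so chi-square is the natural choice of the two named tests. With 20 per group and rates of 75% and 25%, the chi-square test does not reach 95% power. The figure appears to come from a planning formula that belongs to a different test.

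This is the only power figure for the second primary outcome. If it is too high, readers are told that the risk of missing the planned difference is 5% when it is closer to twice that. The stated alpha is also affected: the test that does come near 95% gets there by rejecting too often when there is no difference.

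**Working it through.** **Inputs, all from Protocol section 7.1:** p1 = 0.75, p2 = 0.25, n = 20 per group, two-sided alpha 0.05 (z = 1.960), stated power 95%. The 20 per group is the analysed number, because the section plans at least 30 donors per variant to obtain at least 20 cultures. Each group's variance is 0.75 × 0.25 = 0.1875.

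**Step 1. Reproduce the stated figure.** Normal approximation with unpooled variance:

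- SE = √(2 × 0.1875 / 20) = √0.01875 = 0.1369
- Power = Φ(0.50 / 0.1369 − 1.960) = Φ(1.69) = **95.5%**
- Solved for 95% power: n = (1.960 + 1.645)² × 0.375 / 0.25 = 19.5, so 20 per group

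This fits both the 95% and the 20 per group, so it is the likely source, although the protocol does not say so.

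**Step 2. The formula that matches the chi-square test.** The uncorrected chi-square test uses the pooled variance under the null. The pooled rate is 0.50.

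- Null SE = √(2 × 0.25 / 20) = √0.025 = 0.1581
- Power = Φ((0.50 − 1.960 × 0.1581) / 0.1369) = Φ(0.1901 / 0.1369) = Φ(1.388) = **91.7%**

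**Step 3. Exact power.** List all 21 × 21 pairs of counts, weight each by its binomial probability under 0.75 and 0.25, and add the weights of the pairs that the test rejects. Repeat with equal rates for the type I error.

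| Test at 20 vs 20, two-sided 0.05 | Power, 75% vs 25% | Type I error, 50% vs 50% | Type I error, 25% vs 25% |
|---|---|---|---|
| Chi-square, uncorrected | 90.1% | 4.3% | 5.1% |
| One-way ANOVA of the 0/1 phenotype, two groups | 90.1% | 4.3% | 5.1% |
| Unpooled (Wald) test, not named in the protocol | 94.6% | 8.1% | 6.8% |

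The ANOVA and chi-square rows agree because both statistics depend on the same squared correlation r² between genotype and phenotype: chi-square = 40 r² and F = 38 r² / (1 − r²). At this sample size the two tests reject exactly the same tables.

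**Step 4. A table that shows the difference.** Take 13/20 against 7/20, a difference of 0.30.

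- Unpooled: z = 0.30 / √(2 × 0.65 × 0.35 / 20) = 1.99, p = 0.047
- Chi-square: z = 0.30 / 0.1581 = 1.90, p = 0.058

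The unpooled test counts this result as a success; the named test does not.

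**Step 5. What 95% would need.** With the uncorrected chi-square test, 95% is reached with about a 55-point difference at 20 per group (77.5% vs 22.5%: 95.3%), or with 23 per group at 75% vs 25% (exact 95.2%).

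**Sensitivity only, for variants the protocol does not name:** the continuity-corrected chi-square test has 82.4% power and Fisher's exact test 83.4%.

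**The case against.** The best defence is that the 95% is not an arithmetic slip. A standard two-sided formula gives it from the protocol's own inputs and lands on 20 per group, and approximate formulas are ordinary at the planning stage. This stands as an explanation of where the number came from. It does not make the number true for the named tests at the stated alpha.

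A second route supports 95% for ANOVA. The usual noncentral-F calculation (1 and 38 df, SD = √0.1875 = 0.433) gives 94.5%. That calculation assumes normal data with a fixed SD. The phenotype is 0/1, and what the F test actually does with such data is the 90.1% in the table.

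It is also fair that the power sentence names no test, and that the later sentence covers all comparisons without tying one to this contrast. The link to chi-square is therefore an inference from the binary definition in section 5.1. The conclusion does not depend on it, because both named tests give the same power. A separate analysis plan could fix the test variant, but the power, alpha and candidate tests are all stated in the protocol and do not fit together there.

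Part of the gap comes from discreteness: exact chi-square power is 89.8% at 19 per group, 90.1% at 20 and 92.1% at 21. The smooth pooled formula still leaves a gap of 3.3 points.

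Finally, the effect is modest. Section 7.1 itself admits important limitations in the estimate, and a shift of 3 to 5 points is small beside the uncertainty about the 75% and 25% rates. That stands, and it limits how much weight the point carries.

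**Conclusion.** The concern holds. For 75% against 25% at 20 vs 20 and two-sided 0.05, power is 90.1% exactly for the uncorrected chi-square test and for two-group ANOVA of the 0/1 phenotype, or 91.7% by the pooled formula. The stated 95% is 3 to 5 percentage points too high, and the risk of missing the planned difference is about 8 to 10% rather than 5%. The fault is a mismatch between the planning formula and the analysis test.

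This rests on three assumptions: a yes/no phenotype as section 5.1 defines it, one independent result per donor with 20 analysed donors in each extreme genotype, and no continuity correction. With a correction the power would be lower still (82.4%). The practical consequence is small, because about 90% remains adequate for the planned difference.

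**What to change.** In Protocol section 7.1, restate the power for the second primary outcome as about 90% for the uncorrected chi-square test (75% vs 25%, 20 vs 20, two-sided 0.05), and state how it was calculated. Say explicitly that the test is uncorrected, because the restated figure holds only in that case. If the sponsor intends another test for this comparison, the power reported should be the one for that test.

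The cost is one sentence and a slightly less favourable power figure. The design and the sample size do not change, and the analysis stays within the tests already named.

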## 3.2 Inclusion criteria

Patients of legal age who have given consent to participate in the study will be included and will be listed for the following procedures:

- liver biopsy for suspected nonalcoholic steatohepatitis (NASH) at the time of diagnosis;
- liver resection for hepatocellular carcinoma or other liver lesions (including secondary lesions from other neoplasms and benign focal lesions, which will allow obtaining starting liver tissue

healthy);

- post-transplant healthy liver biopsies;
- cholecystectomies.

You will also be required:

- willingness to sign informed consent for the study
- availability of DNA sample for genetic analysis and clinical data,
- blood sampling for genetic and epigenetic analysis and analysis of non-coding RNAs (lncRNAs, miRNAs and circRNAs).

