## 4. PROCEDURES RELATING TO THE STUDY

### 4.1 Intervention

In collaboration with the Liver Transplant Unit of the Foundation, samples of discarded tissue from patients undergoing liver resection will be collected (both intra-tumoral and extra-tumoral tissues in the case of hepatocarcinoma) or taken from the whole liver post-transplant. This procedure will not entail any additional risk for the patient compared to the usual routine, nor will it reduce the availability of material for standard pathological analyses.

These samples will allow us to isolate cells (ovalocytes – liver progenitor cells) to generate organoids from normal liver tissue (cholecystectomy) and suspected NASH.

We plan to collect up to 20 independent samples per tissue type. The groups considered will be:

- organoids, cultures of sinusoidal stellate cells isolated from 20 patients with CC genotype (I148I)
- organoids, cultures of sinusoidal stellate cells isolated from 20 patients with CG genotype (I148M)
- organoids, cultures of sinusoidal stellate cells isolated from 20 patients with GG genotype

(M148M)

A blood sample (approximately 7 cc) will also be taken, in addition to those already scheduled during regular clinical checks, at the time of surgery or liver biopsy.

It is planned to share a portion of the liver biopsy samples for immunohistochemical analysis to be carried out at the Division of Medicine, Institute for Liver and Digestive Health, University College London, in collaboration with [name], in order to further evaluate the expression of PNPLA3 associated with liver disease, subject to the preparation of an appropriate MTA.

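### Section 7.1 names only single-factor tests for genotype groups meant to mix normal, inflamed/fibrotic and HCC tissue, with no balancing or adjustment for tissue state

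*Protocol*

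**What the plan says.** Section 7.1 gives one sentence on method: "statistical comparisons will be made using the one-way ANOVA or chi-square test, where appropriate". Both tests have a single factor.

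Section 4.1 forms the groups by genotype, for example "organoids, cultures of sinusoidal stellate cells isolated from 20 patients with CC genotype (I148I"), with 20 patients each for CG and GG. Section 7.1 adds that "we estimate to recruit at least 30 donors for each genetic variant", and that the aim is "sufficient representation of the different stages of liver damage (normal liver, inflammation/fibrosis and hepatocellular carcinoma"). It gives no number per stage within a genotype. The nearest thing to a quota is in section 4.1: "We plan to collect up to 20 independent samples per tissue type". That is a ceiling, and it is not crossed with genotype.

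Source tissue varies widely. Section 3.2 admits suspected-NASH biopsies, healthy post-transplant biopsies, cholecystectomies and resections, the last "including secondary lesions from other neoplasms and benign focal lesions, which will allow obtaining starting liver tissue" that is healthy. Section 4.1 takes "both intra-tumoral and extra-tumoral tissues in the case of hepatocarcinoma".

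Primary endpoint 2 (section 5.1) is the impact of I148M on the steatohepatitic phenotype of assembloids. Section 7.1 powers it at 95% for 75% vs 25%, 20 GG against 20 CC, two-sided 0.05. The only stratification stated is by carrier status, for the secondary silencing endpoint.

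**The concern.** Section 1.1 makes two statements that together create the problem. It calls I148M the leading genetic predictor of steatohepatitis and progression, so GG donors may come more often from diseased liver. It also says that organoids can reproduce the healthy or diseased state of the tissue they come from. If both hold here and the stage mix differs by genotype, a test whose only factor is genotype can credit source-tissue state to I148M. If the imbalance runs the other way, it can hide an I148M effect.

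At stake is what a significant result on primary endpoint 2 would mean: an effect of the variant in the cells, or donor disease carried into culture. The silencing and CRISPR work are secondary endpoints and do not answer that for this comparison.

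**Working it through.** **1. The stated power.** Inputs from section 7.1: 75% vs 25%, n = 20 per group, two-sided 0.05.
- Unpooled normal approximation: SE = √(2 × 0.75 × 0.25 / 20) = 0.1369; 0.50 / 0.1369 − 1.960 = 1.691; power = Φ(1.691) = 95.5%. This matches the stated 95%.
- Pooled-variance approximation: 91.7%.
- Exact enumeration of the Pearson chi-square, the test the plan names: 90.1%.

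All three assume one homogeneous phenotype rate per genotype, with no term for tissue state.

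**2. Could the tissue-type ceiling mean balance?** Twenty per genotype within each of three stages would need 20 × 3 × 3 = 180 independent cultures. The protocol plans about 60 subjects (section 6) or 30 × 3 = 90 donors (section 7.1). So stages must be pooled within genotype, in proportions that are not fixed.

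**3. Illustration of the size.** The documents give neither the stage mix nor the carry-over, so both are assumed. There is no genotype effect. Phenotype rates in diseased/healthy sources are 60%/30% (weaker) to 70%/20% (stronger). Each donor's tissue state is random: share s diseased in GG and 1 − s in CC. At s = 0.70:
- Weaker: GG = 0.7 × 0.6 + 0.3 × 0.3 = 0.51; CC = 0.3 × 0.6 + 0.7 × 0.3 = 0.39.
- Stronger: GG = 0.7 × 0.7 + 0.3 × 0.2 = 0.55; CC = 0.3 × 0.7 + 0.7 × 0.2 = 0.35.

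The unadjusted chi-square is enumerated exactly; CMH, stratified by state, is simulated.

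| Diseased share GG/CC | Unadjusted rejects | CMH rejects | CMH power, 75% vs 25% in each stratum |
|---|---|---|---|
| 50/50 | 4.4% | about 5% | 90% |
| 60/40 | 5.9–8.7% | about 5% | 89% |
| 70/30 | 10.7–22.8% | about 5% | 85% |
| 80/20 | 19.1–46.3% | 4–5% | 75% |

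With realised counts held fixed, 12 vs 8 diseased donors gives 4.9–5.4% and 14 vs 6 gives 9.6–19.2% for the unadjusted test.

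**4. Opposite direction.** With the imbalance reversed at 70/30 and a 30-point stage effect, unadjusted power for 75% vs 25% falls from 90% to 66%, while CMH keeps 88%.

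**5. When stratifying misleads.** Assume a 70/30 mix, weak carry-over (+10 points), and an unmeasured factor with 50% prevalence that adds 70 points and is tied to stage with odds ratio 9. From a 10% base rate and with no genotype effect, CMH rejects 10.7% against 4.9% unadjusted.

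**6. Three genotypes.** At 25/50/75% with n = 20 each, a 1-df trend test on allele count has 90% power and the 2-df chi-square 85%.

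**The case against.** The strongest case against has four parts.

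- **An analysis plan may exist.** Covariates are commonly left to it, and the sentence on tests is generic. That limits the point. Still, the protocol itself commits to two single-factor tests, and the stage mix by genotype is settled at recruitment, which a later analysis plan cannot repair.
- **Carry-over may be weak.** The statement that organoids mimic their source is general. Here the cultures start from progenitor cells, are differentiated towards hepatocytes (section 4.2) and have lipid overload induced in vitro (section 4.5). This stands, and it is one reason why no size can be claimed.
- **Mild imbalance does little.** This also stands: at 12 vs 8 the unadjusted test stays near 5%.
- **The unadjusted result may be the intended target.** If I148M drives stage, stage lies partly downstream of genotype, and the 75% vs 25% is anchored to clinical cohorts, which show a total association. For that target, a rejection caused by stage is not simply a false positive. This stands too, and it is why the fix keeps both analyses.

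A reader might go further and derive a diseased share from the yields. Section 7.1 states that "generation efficiency of liver organoids is approximately 100% starting from surgical resections and 33% from biopsies", and 20 cultures from 30 donors would fit 15 of each source (0.33 × 15 + 1.00 × 15 = 19.95), so about a quarter from biopsies. The documents do not support using that as a disease share. Biopsies include healthy post-transplant liver, HCC tissue comes from resections, and no yield is given for cholecystectomy or whole explanted liver. A reader might also want stage terms for the epithelial and stellate compartments separately. At the cell sizes given under the fix, these could hardly be estimated.

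**Conclusion.** The point holds in a limited form and should be acted on. As written, section 7.1 tests genotype alone in groups intended to differ in tissue state, and the protocol shown neither balances nor adjusts for that state. A GG-versus-CC difference could therefore partly reflect source tissue. A reader might infer that the primary result will be biased, or that its false-positive rate is 11% to 23%. The documents do not show that: those figures rest on assumed carry-over and an assumed 70/30 mix, the bias is nil under balance, and its direction is unknown.

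One part needs no such assumption: at the plan's own rates and group sizes, the named chi-square test has about 90% power, and 95% is reached only with the unpooled approximation.

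**What to change.** In section 7.1, for primary endpoint 2:

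1. Add a donor-level GG-versus-CC comparison stratified by the state of the sampled tissue (for example CMH), with normal, inflamed/fibrotic and tumour as strata. Take the state from pathology of the fragment, not from the recruiting procedure. Misclassifying 20% of donors at 70/30 would lift the CMH error rate to 8–14% under the rates assumed above.
2. Report it beside the unadjusted test and name in advance which one carries the 0.05 claim. State that the unadjusted result is the total association and the stratified one the effect at a given tissue state.
3. Restate power as about 90% for the chi-square test, and lower for the stratified test under imbalance (about 85% at 70/30).
4. For the three-genotype comparison, use a 1-df trend test, which matches the dose-related rise that section 7.1 expects.

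Cost: a paragraph, a defined pathology classification and its recording per fragment; no extra patients. Strata will be sparse: 20 / 3 ≈ 6–7 cultures per genotype-by-stage cell, or (20 × 20/30) / 3 ≈ 4–5 if the 60 subjects are counted before culture loss. Power falls if stages are imbalanced, and the stratified result can be biased by unmeasured factors shared by stage and phenotype. Section 1.1 itself points to other genetic and environmental influences. Showing both results guards against relying on either alone.

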
These preclinical studies suggest PNPLA3 as a new therapeutic target, especially with regard to the possibility of reducing its expression in the mutated variant. Therefore, screening based on the determination of the I148M variant status of PNPLA3 could be fundamental for designing future precision medicine approaches. Although the I148M variant of PNPLA3 causes progression of liver damage to advanced fibrosis and hepatocellular carcinoma (1), the phenotypic expression is highly variable and depends on the coexistence of other genetic factors and environmental factors. Furthermore, the relative contribution of the I148M variant carrier state on the steatohepatitis phenotype in

hepatocytes vs. stellate cells is not yet clear. The study of new molecular pharmacological approaches that aim at regulating the expression and activity of PNPLA3 for the prevention and treatment of liver diseases is however still difficult, due to both the limitations of experimental models in animals (cost, suffering, different regulation of lipid metabolism and PNPLA3 compared to humans) and the difficulty of reproducing NASH in models *in vitro*.

The current models *in vitro*, based on liver cell lines, are in fact unable to reproduce the intrinsic cellular heterogeneity, the three-dimensional architecture of the tissue and the cell-cell interactions. These characteristics are fundamental in the study of the processes that can lead to the onset of steatosis, progressing to a fibrotic, cirrhotic and tumorous state following an external insult.

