## 2. OBJECTIVE OF THE EXPERIMENT

The aim of this project is to study the cellular and molecular mechanisms through which the variant at risk of PNPLA3 (148M) accelerates the progression of liver damage in models based on the development of liver organoids and assembloids, and to test in these the efficacy of new molecular pharmacological approaches aimed at silencing the expression of the mutated protein variant in improving the pathological phenotype. Our hypothesis is that the loss of function of PNPLA3 in hepatocytes and hepatic stellate cells may represent a link between accumulation of hepatic fat, development of lipotoxicity and inflammation, fibrosis and finally liver cancer. The 148M variant could determine a persistent and uncontrolled activation of stellate cells (HSCs) due to an altered ability to release retinol. Activated HSCs would then undergo premature senescence with consequent release of pro-inflammatory and carcinogenic mediators. Silencing of PNPLA3 by using antisense RNA would therefore lead to a greater improvement of the

hepatocellular damage specifically in models derived from cells carrying the risk variant.

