#### 4.3 Isolation and culture of sinusoidal stellate cells

A part of the biopsy fragments or those obtained from surgical resections, once digested to obtain the epithelial cells that will form the organoids, will be processed to obtain hepatic stellate cells (HSC) and sinusoidal cells (LSEC). The latter will be isolated by exploiting their low density, due to the presence of lipid droplets that characterize them. The stellate cells will be cultured on plastic and we will characterize their activation state and the purity of the cell population, by flow cytometry and quantitative Real Time PCR (RT-qPCR), evaluating the presence of the

retinol and specific cellular markers (15). Sinusoidal cells will be cultured on plastic pre-treated with a fibronectin coating and grown in the presence of the growth factor VEGF.

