#### 4.4 Generation of assemblyloids

In order to obtain the assemblyloids, both the organoids and the stellate and sinusoidal cells will be dissociated into single cells by enzymatic digestion using trypsin. The cells will then be included in reduced growth factor Matrigel in different ratios in order to mimic the physiological conditions present in the liver tissue. Once the Matrigel has polymerized, the culture medium appropriately formulated to allow the survival of both hepatocytes, ductal cells and stellate cells will be added: Advanced DMEM/F12 supplemented with 1% N2 and 1% B27 (both from GIBCO), 1.25 mM N-Acetylcysteine (Sigma), 10 nM Leu-Gastrin (Sigma), 50 ng/ml EGF (Peprotech), 25 ng/ml HGF (Peprotech) and 2% FBS (GIBCO).

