### Secondary Endpoints

- Knowledge of the behavioral and morphological differences between physiological and NASH hepatocytes and stellate cells.
  - Detection of new biomarkers predictive of the development and progression of the disease.
- a. - Analysis of epigenetic differences in physiological conditions, onset and progression of NASH.

- Knowledge of the molecular mechanisms underlying cellular-level observations using "omics" scale assessments and CRISPR-Cas9 genetic engineering.
- Analysis of the impact of PNPLA3 silencing on the steatohepatitis phenotype of human liver assembloids, stratified by I148M variant carrier status in epithelial cells vs. stellate cells.

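### Section 7.1 names only tests that assume independent results, which is not the best choice where crossed or silenced assembloids will probably share donors

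*Protocol*

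**What the plan says.** Section 7.1 fixes the comparative methods in one sentence: "statistical comparisons will be made using the one-way ANOVA or chi-square test, where appropriate", with significance at P < 0.05. The sample-size text above it powers one contrast, 75% against 25% steatohepatitis phenotype in 20 homozygous risk-variant donors against 20 wild-type, and states 95% power.

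Two other endpoints have a different structure.

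- **Crossed combinations.** Primary endpoint 2 (section 5.1) asks for the impact of I148M with "evaluation of possible combinations both in epithelial cells - hepatocytes and in stellate cells". Section 1.1 gives the motive: "the relative contribution of the I148M variant carrier state on the steatohepatitis phenotype in" hepatocytes versus stellate cells is described as unclear.
- **Silencing.** A secondary endpoint studies PNPLA3 silencing "stratified by I148M variant carrier status in epithelial cells vs. stellate cells". Section 2 expects a greater improvement of "hepatocellular damage specifically in models derived from cells carrying the risk variant", which is a hypothesis about a difference in benefit between genotypes.

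On the material, section 4.3 takes stellate cells from the same fragments, "once digested to obtain the epithelial cells that will form the organoids, will be processed to obtain hepatic stellate cells". Section 4.4 says that "both the organoids and the stellate and sinusoidal cells will be dissociated into single cells by enzymatic digestion using trypsin" and then recombined, but not whether the two cell types come from one donor or two. Section 6 expects about 60 subjects. Section 7.1 counts more than 10^3 organoids per individual. CRISPR-Cas9 editing appears among the secondary endpoints.

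**The concern.** The phrase about appropriateness in 7.1 chooses between two tests that both need independent results. It does not bring in a paired, two-factor or donor-effect analysis.

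An assembloid built from one donor carries one germline genotype in both cell types, so no analysis of such assembloids can say which cell type carries the effect. That question needs assembloids crossed between donors, or edited lines. Crossing three genotypes by three with about 60 donors makes reuse of lines likely. For silencing, the natural experiment splits one donor's material into silenced and unsilenced halves.

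If results that share a donor are analysed as independent, the error depends on the layout. Unpaired analysis of a split-donor experiment is conservative and loses power. Repeated use of lines in a between-genotype comparison can give too many false positives. At stake are the attribution to a cell type, within a primary endpoint, and the test of the study's therapeutic hypothesis.

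**Working it through.** **1. The plan's own figure.** Inputs from 7.1: 75% against 25%, 20 per group, two-sided alpha 0.05. With unpooled variance, SE = sqrt(2 × 0.75 × 0.25 / 20) = 0.137; 0.5/0.137 = 3.65; 3.65 − 1.96 = 1.69; power 95.5%. This reproduces the stated 95%. The pooled formula gives 91.7%, and the exact power of the uncorrected chi-square is 90.1%. Every version assumes one independent result per donor, which this contrast can satisfy, so the present point leaves it untouched.

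**2. Is sharing likely?** Three genotypes in each of two cell types give up to 9 combinations. With each of 60 donors used once, a combination holds 60/9 = 6.7 assembloids. Keeping 20 per combination (an assumption borrowed from 7.1's group size) needs 9 × 20 = 180 assembloids, so each donor's line is used 180/60 = 3 times. This is inference; no section states the layout.

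**3. Silencing by genotype.** Assumptions: continuous outcome with SD 1, 20 GG and 20 CC donors, one silenced and one unsilenced result each, benefit differing by 0.5 SD, within-donor correlation r. The protocol gives none of the last three.

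- True SE of the difference in benefit: sqrt(4(1 − r)/20).
- SE that an unpaired analysis uses: sqrt(4/20) = 0.447, so it rejects beyond 1.96 × 0.447 = 0.876.
- Example at r = 0.5: true SE = 0.316. Unpaired: (0.876 − 0.5)/0.316 = 1.19, power 11.7%. Within donor: 0.5/0.316 = 1.58, and 1.96 − 1.58 = 0.38, power 35%.

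Simulation (20,000 runs) agrees:

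| r | Unpaired power | Within-donor power | Share of power lost | Unpaired type I error |
|---|---|---|---|---|
| 0.3 | 15.5% | 25.3% | 1 − 15.5/25.3 = 39% | 2.2% |
| 0.5 | 12.0% | 34.8% | 1 − 12.0/34.8 = 66% | 0.7% |
| 0.7 | 6.8% | 51.1% | 1 − 6.8/51.1 = 87% | 0.1% |

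The within-donor analysis holds its type I error at about 5%.

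**4. Crossed combinations with reuse.** Assumptions: 20 lines per genotype and cell type, each line used once with each genotype of the other cell type, and each cell type's donor accounting for a share v of total variance. Stellate donor effects then cancel between epithelial genotypes. With m uses per line, the true variance of an epithelial-genotype mean, relative to what the naive test assumes, is about m·v + (1 − 2v) = 1 + (m − 2)v.

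- m = 2 (CC and GG only): the ratio is 1, so no inflation is expected. Simulated: 5.1-5.5% by ANOVA, 5.1-6.3% by chi-square.
- m = 3 (three genotypes): the ratio is 1 + v. On 2 df the type I error is about exp(−5.991/(2(1 + v))).

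| v | Formula | ANOVA, simulated | Chi-square on yes/no phenotype, simulated |
|---|---|---|---|
| 0.05 | 5.8% | 5.6% | 5.5% |
| 0.15 | 7.4% | 7.2% | 5.6% |
| 0.25 | 9.1% | 9.5% | 7.3% |
| 0.40 | 11.8% | 12.4% | 9.2% |

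An additive two-factor model with crossed donor effects gave 4.3/5.7/3.8% at v = 0.15/0.25/0.40 on the continuous outcome, and 5.2/5.5/4.0% when fitted linearly to the 0/1 result (600 runs, Monte Carlo error about 0.9 points).

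**5. Crossed combinations without reuse.** With 60 assembloids from different donors and an epithelial-only effect of 25/50/75% (the 50% is assumed), chi-square per factor has 84.7% power and the two-factor model 86.1% at the same coding. The named test is adequate there.

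**The case against.** The strongest reply is that 7.1 already thinks in donors. It asks for independent cultures and sets 20 cases against 20 controls, and section 4.1 counts groups in patients. Pairing and random effects are often left to an analysis plan, which may exist. The named tests also permit valid analyses: chi-square for GG against CC, and one-way ANOVA applied to within-donor changes. Much of this stands and limits the point. What remains is that 7.1 does name its tests, both in a form that assumes independence, and does not carry the donor over into the analysis sentence for two endpoints where it matters.

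The sizes are also open to challenge. Reuse is inferred, the correlations are assumed, inflation is negligible at low donor share or in the CC/GG-only layout, and the unpaired silencing analysis errs on the safe side. The silencing figures use a continuous outcome; a yes/no version was not simulated, nor was a logistic mixed model under reuse. These limits are accepted.

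A reader might also infer that one patient supplies two cultures to the same group, because section 4.1 collects "both intra-tumoral and extra-tumoral tissues in the case of hepatocarcinoma". The protocol does not support this. It plans independent samples per tissue type and counts the genotype groups in patients, and nothing pools tumour and non-tumour tissue from one patient in one genotype group. Nor does it propose a single omnibus test over all nine combinations.

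**Conclusion.** The point holds as a recommended improvement. The plan names two tests that suit its powered contrast but are not the best choice for crossed combinations and for silencing by genotype, where donors will probably be shared.

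For silencing, unpaired analysis would lose roughly 40% of the power at a within-donor correlation of 0.3 and most of it at 0.5 or more. For three crossed genotypes with three uses per line, type I error for epithelial genotype would be about 6-12% by ANOVA and 5-9% by chi-square at donor shares of 0.05-0.40. With two genotypes and two uses there is almost no inflation. All of this depends on donor sharing, correlations, donor shares and a 0.5 SD difference that the protocol does not give.

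Two stronger readings do not follow. The stated 95% power is not undermined by this point, since that contrast can use one result per donor. And ignoring donors does not always produce false positives: in the silencing comparison it does the reverse.

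**What to change.** Keep chi-square for GG against CC with one result per donor, and add to 7.1:

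> The donor is the independent unit and technical replicates are averaged. When silenced and unsilenced assembloids share donors, within-donor differences are compared across genotypes. Crossed combinations are analysed with an additive two-factor model (epithelial and stellate genotype), with random effects for epithelial and stellate donor when lines are reused.

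In 4.4 and 4.5, state whether donor lines are reused, and that attribution to a cell type is drawn only from crossed or edited assembloids, since same-donor assembloids carry one genotype in both cell types.

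The cost is a few sentences and a little more analysis work in R, which 7.1 already names. No extra donors or samples are needed. If donors turn out not to be shared, the added sentences cost almost nothing.
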